5 PROCEDURES

5.1 Study procedures. Using lay language, provide a complete description of the study procedures, including the sequence, intervention or manipulation (if any), drug dosing information (if any), use of records, time required, and setting/location. If it is available and you think it would be helpful to the IRB: Upload a study flow sheet or table to the **Supporting Documents** SmartForm in **Zipline**.

For studies comparing standards of care: It is important to accurately identify the research procedures. See UW IRB [POLICY: Risks of Harm from Standard Care](#) and the draft guidance from the federal Office of Human Research Protections, ["Guidance on Disclosing Reasonably Foreseeable Risks in Research Evaluating Standards of Care"](#), October 20, 2014.

All participants will undergo instrumented motion analysis in the Computational, Robotics, and Experimental Biomechanics Laboratory at the University of Washington Medical Center. After consent has been obtained and demographic details recorded, participants will be given the opportunity to warm up by stretching and walking or jogging on a treadmill for a few minutes.

Reflective markers will then be placed on the body to track the movement of limb segments. Electrodes will be placed over the quadriceps and hamstring muscles and will be used to measure the activation of these muscle. Ground reaction forces will be measured during testing using force plates embedded in the floor. A blood pressure restriction cuff, similar to the type of cuff used to obtain blood pressure measurements from the arm, connected to the blood flow restriction system will be placed around the thigh. The level of blood flow restriction is measured in terms of limb occlusion pressure (LOP). When having a blood pressure measurement taken using a cuff around the arm, the highest pressure the cuff is inflated to will be approximately 100% LOP. During blood flow restriction, the participant will feel a similar pressure around the thigh while the system calibrates, then a lesser pressure during the exercises.

Guided by an experienced physiotherapist and after a short warm-up, the participant will be asked to perform a series of exercises using their injured leg in the case of the ACL group, or randomly chosen for the controls. The exercise is step up and step down from a 30cm high step. Each exercise will be performed 30 times, then a 30 second break followed by 3 sets of 15 repetitions with a 30 second break. This is the standard protocol for these rehabilitation exercises. Up to four conditions will be tested: 1) no BFR; 2) 80% LOP; 2) 60% LOP; 3) 40% LOP. The order of conditions will be randomized between participants. After each exercise is complete, participants will be asked to rate the difficulty and discomfort associated with performing each exercise on numerical analogue scales (0 – no difficulty/discomfort; 10: extremely difficult/uncomfortable). Participants will be given as much rest as needed between exercises.

The visit will not replace one of the participants standard rehab visits but participation in the study will be noted in the participant's medical record.

5.2 Data variables. Describe the specific data you will obtain (including a description of the most sensitive items). If you would prefer, you may upload a list of the data variables to the **Supporting Documents** SmartForm instead of describing the variables below.

Kinematic and kinetic variables from the motion capture system; muscle activity; date of birth, weight, height, sex, time since injury,

5.3 Data sources. For all types of data that you will access or collect for this research: Identify whether you are obtaining the data from the subjects (or subjects' specimens) or whether you are obtaining the data from some other source (and identify the source).

If you have already provided this information in Question 5.1, you do not need to repeat the information here.

All data will be collected from the subject.

5.4 Retrospective/prospective. For all types of data and specimens that you will access or collect for this research: do all data and specimens to be used in the research exist (for example, in subjects' medical records) at the time this application is being submitted for initial review?

	No
	Yes

Include any necessary comments or explanation below (Note that for most studies this can be left blank):

5.5 Identifiability of data and specimens. Answer these questions carefully and completely. This will allow HSD to accurately determine the type of review that is required and to assist you in identifying relevant compliance requirements. Review the following definitions before answering the questions:

Access means to view or perceive data, but not to possess or record it. See, in contrast, the definition of "obtain".

Identifiable means that the identity of an individual is or may be readily (1) ascertained by the researcher or any other member of the study team from specific data variables or from a combination of data variables, or (2) associated with the information.

Direct identifiers are direct links between a subject and data/specimens. Examples include (but are not limited to): name, date of birth, medical record number, email or IP address, pathology or surgery accession number, student number, or a collection of your data that is (when taken together) identifiable.

Indirect identifiers are information that links between direct identifiers and data/specimens. Examples: a subject code or pseudonym.

Key refers to a single place where direct identifiers and indirect identifiers are linked together so that, for example, coded data can be identified as relating to a specific person. Example: a master list that contains the data code and the identifiers linked to the codes.

Obtain means to possess or record in any fashion (writing, electronic document, video, email, voice recording, etc.) for research purposes and to retain for any length of time. This is different from **accessing**, which means to view or perceive data.

a. Will you or any members of your team have access to any direct or indirect identifiers?

Yes

→ If yes, describe which identifiers and for which data/specimens.

Names and medical records to determine if they have had an ACL reconstruction

No

→ If no, select the reason(s) why you (and all members of your team) will not have access to direct or indirect identifiers.

There will be no identifiers.

Identifiers or the key have been (or will have been) destroyed before you have access.

You have (or will have) entered into an agreement with the holder of the identifiers (or key) that prohibits the release of the identifiers (or key) to you under any circumstances.

You should be able to produce this agreement for IRB upon request. Examples: a Data Use Agreement, Repository Gatekeeping form, or documented email.

There are written policies and procedures for the repository/database/data management center that prohibit the release of the identifiers (or identifying link). This includes situations involving an Honest Broker.

There are other legal requirements prohibiting the release of the identifiers or key to you. Describe them below.

b. Will you obtain any direct or indirect identifiers?

→ If yes, describe which identifiers and for which data/specimens.

Names and medical record numbers and email and/or phone number for contact

→ If no, select the reason(s) why you (and all members of your team) will not obtain direct or indirect identifiers.

There will be no identifiers.

Identifiers or the key have been (or will have been) destroyed before you have access.

You have (or will have) entered into an agreement with the holder of the identifiers (or key) that prohibits the release of the identifiers (or key) to you under any circumstances.

You should be able to produce this agreement for IRB upon request. Examples: a Data Use Agreement, Repository Gatekeeping form, or documented email.

There are written policies and procedures for the repository/database/data management center that prohibit the release of the identifiers (or identifying link). This includes situations involving an Honest Broker.

There are other legal requirements prohibiting the release of the identifiers or key to you. Describe them below.

c. If you obtain any identifiers, indicate how the identifiers will be stored (and for which data). NOTE: Do not describe your data security plan here – we will ask for that information in section 9.6.

You will store the identifiers with the data. Describe the data to which this applies:

You will store identifiers and study data separately but you will maintain a link between the identifiers and the study data (for example, through the use of a code). Describe the data to which this applies:

Upon enrollment into the study, the participant will be assigned a unique identifier of the form "PBFRxxx" where "xxx" are sequential numbers 001, 002, ... 030. Data identified using these IDs will be stored separately from any personal information that could identify the individual. All de-identified data will be stored on password protected computers in the Computational, Robotic, and Experimental Biomechanics laboratory. Names and contact details will be kept separately in a locked filing cabinet, room BB1002.

You will store identifiers separately from the study data, with no link between the identifiers and the study data. Describe the data to which this applies:

d. Research collaboration. Will individuals who provide you with coded information or specimens for your research also collaborate on other activities for this research? If yes, identify the activities and provide the name of the collaborator's institution/organization.

Examples include but are not limited to: (1) study, interpretation, or analysis of the data that results from the coded information or specimens; and (2) authorship on presentations or manuscripts related to this work.

No

5.6 Newborn dried blood spots. Will you use newborn dried bloodspots collected in the United States on or after March 18, 2015?

	No
-------------------------------------	----

No

Yes → If yes, is this research supported by any federal funding (including any fellowship or career development award that provides salary support)?

	No
--------------------------	----

No

	Yes
--------------------------	-----

Yes

→ If yes, describe how you will ensure that the bloodspots were collected with parental permission (in compliance with a 2015 law that applies to federal-funded research).

5.7 Protected Health Information (PHI). Will you access, obtain, use, or disclose a participant's identifiable PHI for any reason (for example, to identify or screen potential subjects, to obtain study data or specimens, for study follow-up) that does not involve the creation or obtaining of a Limited Data Set?

PHI is individually-identifiable healthcare record information or clinical specimens from an organization considered a "covered entity" by federal HIPAA regulations, in any form or media, whether electronic, paper, or oral. If you will use UW Medical Records, you must answer yes to this question.

	No
--------------------------	----

No → If no, skip the rest of this question; go to [question 5.8](#)

	Yes
-------------------------------------	-----

Yes → If yes, answer all of the questions below.

a. Describe the PHI you will access or obtain, and the reason for obtaining it. *Be specific.*

To screen potential subjects, the clinic schedule of patients undergoing rehabilitation after ACL reconstruction will be accessed to determine potential participants. Additionally, a review of clinic schedule medical records to verify eligibility may occur.

b. Is any of the PHI located in Washington State?

	No
--------------------------	----

No

	Yes
-------------------------------------	-----

Yes

c. Describe how you will access or obtain the PHI. *Be specific.*

[name] will access their own clinic schedules as well as medical records of potential subjects.

d. For which PHI will you obtain HIPAA authorization from the subjects by having them sign a HIPAA Authorization form, before obtaining and using the PHI?

All ACL-R subjects will sign a HIPAA authorization prior to obtaining name, surgical procedure, and surgery date.

Confirm by checking the box that you will use the UW Medicine [HIPAA Authorization](#) form maintained on the HSD website if you will access, obtain, use, or disclose UW Medicine PHI.

Confirmed

e. For which PHI will you NOT obtain HIPAA authorization from the subjects?

Type of surgery, date of surgery, progress of rehabilitation.

Provide the following assurances by checking the boxes.

The PHI will not be reused or disclosed to any other person or entity, except as required by law, for authorized oversight of the research study, or for other research for which the use or disclosure of PHI would be permitted.

You will fulfill the HIPAA “accounting for disclosures” requirement. See [UW Medicine Privacy Policy #25](#). THIS IS ONLY FOR UW RECORDS.

There will be reasonable safeguards to protect against identifying, directly or indirectly, any patient in any report of the research.

5.8 Genomic data sharing. Will you obtain or generate genomic data (as defined at <http://osp.od.nih.gov/scientific-sharing/genomic-data-sharing-faqs/>)?

No
 Yes

→ If yes, answer the question below.

a. Do you plan to send genomic data from this research to a national database (for example, NIH's dbGaP database)?

No
 Yes → If yes, complete the [ZIPLINE SUPPLEMENT Genomic Data Sharing](#) and upload it to the **Supporting Documents** SmartForm of **Zipline**.

5.9 Whole genome sequencing. For research involving biospecimens: Will the research include whole genome sequencing?

Whole genome sequencing is sequencing of a human germline or somatic specimen with the intent to generate the genome or exome sequence of that specimen.

No
 Yes

5.10 Data and specimen sharing/banking. Are you likely to share some or all of the data, specimens, or subject contact information with other researchers or a repository/database for research purposes not related to this study, or to bank them for your own future unspecified research uses? **You are strongly encouraged to consider the broadest possible future plans you might have, and whether you will obtain consent now from the subjects for future sharing or unspecified uses.** Answer **YES** even if you will only share information without identifiers. Answer **NO** if you are unlikely to do any sharing, or if your only sharing will be through the NIH Genomic Data Sharing described in [question 5.8](#).

Many federal grants and contracts now require data or specimen sharing as a condition of funding, and many journals require data sharing as a condition of publication. "Sharing" may include: informal arrangements to share your banked data/specimens with other investigators; establishing a repository from which you formally share with others through written agreements; or sending your data/specimens to a third party repository/archive/entity such as the Social Science Open Access Repository (SSOAR), or the UCLA Ethnomusicology Archive.

	No
	Yes

→ If yes, answer all of the questions below.

a. Describe what will be stored, including whether any direct or indirect (e.g., subject codes) identifiers will be stored.

All data collected during this study will be placed in a deidentified research repository

b. Describe what will be shared, including whether direct identifiers will be shared and (for specimens) what data will be released with the specimens.

No direct identifiers will be shared but all other deidentified data will be shared

c. Who will oversee and/or manage the sharing?

[name]

d. Describe the possible future uses, including limitations or restrictions (if any) on future uses or users. As stated above, consider the broadest possible uses.

Examples: data will be used only for cardiovascular research; data will not be used for research on population origins.

Data will be used only for musculoskeletal research related to rehabilitation

e. Consent. Will you obtain consent now from subjects for the banking and/or future sharing?

	No
	Yes

→ If yes, be sure to include the information about this consent process in the consent form (if there is one) and in your answers to the consent questions in [Section 8](#).

f. Withdrawal. Will subjects be able to withdraw their data/specimens from banking or sharing?

	No
	Yes

→ If yes, describe how, and whether there are any limitations on withdrawal.

Example: data can be withdrawn from the repository but cannot be retrieved after they are released.

g. Agreements for sharing or release. Confirm by checking the box that you will comply with UW (and, if applicable, UW Medicine) policies that require a formal agreement between you and the recipient for release of data or specimens to individuals or entities other than federal databases.

Data Use Agreements or Gatekeeping forms are used for data; Material Transfer Agreements are used for specimens (or specimens plus data). Do not attach your template agreement forms; the IRB neither reviews nor approves them

Confirmed

5.11 Communication with subjects during the study. Describe the types of communication (if any) you will have with already-enrolled subjects during the study. Provide a description instead of the actual materials themselves.

Examples: email, texts, phone, or letter reminders about appointments or about returning study materials such as a questionnaire; requests to confirm contact information.

Subjects will be asked if they prefer to be contacted via phone or email. Communication will consist of visit reminders.

5.12 Future contact with subjects. Do you plan to retain any contact information you obtain for your subjects so that they can be contacted in the future?

No
 Yes

→ If yes, describe the purpose of the future contact, and whether use of the contact information will be limited to your team; if not, describe who else could be provided with the contact information. Describe your criteria for approving requests for the information.

Examples: inform subjects about other studies; ask subjects for additional information or medical record access that is not currently part of the study proposed in this application; obtain another sample.

5.13 Alternatives to participation. Are there any alternative procedures or treatments that might be advantageous to the subjects?

If there are no alternative procedures or treatments, select "No". Examples of advantageous alternatives: earning extra class credit in some time-equivalent way other than research participation; obtaining supportive care or a standard clinical treatment from a health care provider instead of participating in research with an experimental drug.

No
 Yes → If yes, describe the alternatives.

5.14 Upload to the Supporting Documents SmartForm of **Zipline** all data collection forms (if any) that will be directly used by or with the subjects, and any scripts/talking points you will use to collect the data. Do not include data collection forms that will be used to abstract data from other sources (such as medical or academic records, or video recordings).

- **Examples:** survey, questionnaires, subject logs or diaries, focus group questions.
- **NOTE:** Sometimes the IRB can approve the general content of surveys and other data collection instruments rather than the specific form itself. This prevents the need to submit a modification request for future minor changes that do not add new topics or increase the sensitivity of the questions. To request this general approval, use the text box below to identify the questionnaires/surveys/ etc. for which you are seeking this more general approval. Then briefly describe the scope of the topics you will cover and the most personal and sensitive questions. The HSD staff person who screens this application will let you know whether this is sufficient or whether you will need to provide more information.
- **For materials that cannot be uploaded:** upload screenshots or written descriptions that are sufficient to enable the IRB to understand the types of data that will be collected and the nature of the experience for the participant. You may also provide URLs (website addresses) or written descriptions below. Examples of materials that usually cannot be uploaded: mobile apps; computer-administered test; licensed and restricted standardized tests.
- **For data that will be gathered in an evolving way:** This refers to data collection/questions that are not pre-determined but rather are shaped during interactions with participants in response to observations and responses made during those interactions. If this applies to your research, provide a description of the process by which you will establish the data collection/questions as you interact with subjects, how you will document your data collection/questions, the topics you plan to address, the most sensitive type of information you will plan to gather, and the limitations (if any) on topics you will raise or pursue.

Use this text box (if desired) to provide:

- Short written descriptions of materials that cannot be uploaded, such as URLs
- A description of the process you will use for data that will be gathered in an evolving way.
- The general content of questionnaires, surveys and similar instruments for which you are seeking general approval. (See the **NOTE** bullet point in the instructions above.)

5.15 Send HSD a Confidentiality Agreement if you will obtain or use any private identifiable UW records without subject's written consent (for example, screening medical records or class grades to identify possible subjects).

The Confidentiality Agreement form must be completed, printed, signed, and mailed to the Human Subjects Division at Box 359470. Your IRB application cannot be approved until we receive the Confidentiality Agreement.

6 CHILDREN (MINORS) and PARENTAL PERMISSION

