c. Comprehension. Describe how you will ensure or test the subjects' understanding of the information during the consent process.

After reading the consent form, participants will be asked if they know the study is voluntary and if they understand the procedures involved.

d. Influence. Does your research involve any subject groups that might find it difficult to say "no" to your research because of the setting or their relationship with you, even if you don't pressure them to participate?

Examples: Student participants being recruited into their teacher's research; patients being recruited into their healthcare provider's research, study team members who are participants; outpatients recruited from an outpatient surgery waiting room just prior to their surgery.

No

Yes

→ If yes, describe what you will do, for each of these subject groups, to reduce any effect of the setting or relationship on their decision.

Examples: a study coordinator will obtain consent instead of the subjects' physician; the researcher will not know which subjects agreed to participate; subjects will have two days to decide after hearing about the study.

ACL-R participants will be asked by their clinical provider if they are interested in taking part in a research study. If yes, they will talk to non-clinical study team members in a private room where they will be given an opportunity to ask questions and to take home the consent form to further consider participation. Members of the study team who are not involved with the clinical care of the participant will meet with the participants. Clinical providers will not obtain consent.

e. **Ongoing process.** For research that involves multiple or continued interaction with subjects over time, describe the opportunities (if any) you will give subjects to ask questions or to change their minds about participating.

This study involves a single visit where both consent and measurements will be obtained.

8.3 Written documentation of consent. Which of the statements below describe whether you will obtain documentation of consent? NOTE: This question does not apply to screening and recruiting procedures which have already been addressed in [question 4.6](#).

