10 RISK / BENEFIT ASSESSMENT

10.1 **Anticipated risks.** Describe the reasonably foreseeable risks of harm, discomforts, and hazards to the subjects and others of the research procedures. For each harm, discomfort, or hazard:

- Describe the magnitude, probability, duration, and/or reversibility of the harm, discomfort, or hazard, AND
- Describe how you will manage or reduce the risks. Do not describe data security protections here, these are already described in Question 9.6.
- Consider possible physical, psychological, social, legal, and economic harms, including possible negative effects on financial standing, employability, insurability, educational advancement or reputation. For example, a breach of confidentiality might have these effects.
- Examples of "others": embryo, fetus, or nursing child; family members; a specific group.
- Do not include the risks of non-research procedures that are already being performed.
- If the study design specifies that subjects will be assigned to a specific condition or intervention, then the condition or intervention is a research procedure - even if it is a standard of care.
- Examples of mitigation strategies: inclusion/exclusion criteria; applying appropriate data security measures to prevent unauthorized access to individually identifiable data; coding data; taking blood samples to monitor something that indicates drug toxicity.
- As with all questions on this application, you may refer to uploaded documents.

- Risk of breach of confidentiality.
- Risk of fatigue or soreness during and after carrying out the exercises.
- The blood flow restriction device applies constrictive pressure to the thigh and can cause minor and transient discomfort. The time the cuff is inflated is minimized during testing (no longer than 20 minutes over the test period, divided into 6-7 minute intervals)
- The use of reflective markers and muscle sensors may cause some skin irritation which is usually minor and resolves quickly.

The participant will be encouraged to report any discomfort or pain beyond acceptable levels and at sites other than where the pressure cuff is applied at any point during testing. After each set of exercises, a researcher will ask the participant to confirm that they are happy to continue the study.

10.2 **Reproductive risks.** Are there any risks of the study procedures to men and women (who are subjects, or partner of subjects) related to pregnancy, fertility, lactation or effects on a fetus or neonate?

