NCT04635579

Personalized Blood Flow Restriction for Anterior Cruciate Ligament Rehabilitation

04/24/2018

Statistical Analysis

For the biomechanical variables, two primary sets of statistical comparisons were performed. First, the healthy and anterior cruciate ligament reconstruction (ACLR) group were compared to each other for the final set of step-ups during both the control and personalized blood flow restriction (PBFR) exercise conditions. Then, both groups were compared between the control and PBFR conditions for the same timepoint (repeated measures). Statistical parametric mapping a technique which allows the temporal data such as that collected during this type of biomechanical study to be compared, was used to test for statistically significant differences between the kinematic and kinetic waveforms. This approach allowed the full dataset to be compared, rather than looking at discrete values such as the peak range of motion. The significance level was adjusted to $\alpha = 0.001$ to account for multiple comparisons. Descriptive statistics were calculated for the peak movement for all motions. Participant reported scores for difficulty and discomfort were compared using Wilcoxon signed-rank tests (between exercise conditions) and Wilcoxon rank-sum tests (within exercise conditions). Data were analyzed using R V3.5.2 and Python 2.7. Figures were produced using the ggplot2 package.

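### The within-person comparisons of control with PBFR ignore the position of each condition in the randomised order, which costs precision if performance drifts over the visit

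*Protocol*

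**What the plan says.** Protocol section 5.1 sets out the conditions: "Up to four conditions will be tested: 1) no BFR; 2) 80% LOP; 2) 60% LOP; 3) 40% LOP". The load within each is given as "Each exercise will be performed 30 times, then a 30 second break followed by 3 sets of 15 repetitions with a 30 second break", which is 30 + 3 × 15 = 75 repetitions. On sequence it says "The order of conditions will be randomized between participants", and on recovery "Participants will be given as much rest as needed between exercises". No minimum rest, recovery criterion or balanced order list is described. Section 8.2(e) confirms that everything happens on one day: "This study involves a single visit where both consent and measurements will be obtained". Section 10.1 lists among the risks "Risk of fatigue or soreness during and after carrying out the exercises".

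The SAP, under Statistical Analysis, says that "both groups were compared between the control and PBFR conditions for the same timepoint (repeated measures", the timepoint being the final set of step-ups. SPM is used at alpha 0.001. Difficulty and discomfort ratings are compared between conditions by Wilcoxon signed-rank tests. The SAP names no term for order, period, sequence or carry-over, and no check for them. It refers to a single PBFR condition, without saying which restriction level it is or how many conditions were run.

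**The concern.** Hypothesis H2 in Protocol section 1.5 (less stability with restriction) rests on a within-person contrast. Up to 4 × 75 = 300 repetitions on one leg in one visit could change performance from block to block, through fatigue or through practice. If so, part of each person's control-minus-PBFR difference reflects only which condition came later. A plain paired comparison leaves that part in the error term, although the order is known and could be used to remove it. The loss matters more than usual here because alpha is 0.001. H2 predicts a difference, so lost power makes a reassuring null result more likely.

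A second mechanism is distinct. Residual effects of one block may persist into the next. If they differ by condition, randomising the order does not cancel them.

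**Working it through.** The documents give no effect size, SD, power or sample-size derivation, so there is no stated figure to reproduce.

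**Inputs from the documents:** up to four conditions in randomised order in one visit (Protocol 5.1, 8.2(e)); at most 30 people per group (Protocol 2.7); alpha 0.001 (SAP).

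**Assumptions:** all orders equally likely; each group tested separately with n = 30; two-sided test; SD of the paired difference 1 without drift; true effect 0.7 SD; linear drift of b SD per block, b = 0.1 to 0.5; a scalar paired t-test standing in for SPM.

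**1. Drift: bias.** Over the 24 orders of four conditions, the mean difference in position between any two conditions is 0. The same is true of the two orders of two conditions. Expected bias is therefore exactly zero. In simulation with no true effect and b = 0.5 (four conditions), the signed-rank test rejected 4.9% of the time at a nominal 5%.

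**2. Drift: variance.** Among the 24 orders, control and a given restricted condition are 1, 2 or 3 positions apart in 12, 8 and 4 orders. The variance of the position difference is (12×1 + 8×4 + 4×9)/24 = 80/24 = 3.33. With two conditions it is 1.0. The variance of the paired difference becomes 1 + 3.33b² or 1 + 1.0b², and the effective n is 30 divided by that. Power is from the noncentral t with 29 df and noncentrality 0.7 × √30 / √variance.

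| b | Variance (four) | Effective n | Power | Variance (two) | Effective n | Power |
|---|---|---|---|---|---|---|
| 0 | 1.00 | 30 | 57% | 1.00 | 30 | 57% |
| 0.1 | 1.03 | 29.0 | 55% | 1.01 | 29.7 | 57% |
| 0.3 | 1.30 | 23.1 | 41% | 1.09 | 27.5 | 52% |
| 0.5 | 1.83 | 16.4 | 24% | 1.25 | 24.0 | 43% |

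**3. What a position term recovers.** Simulated power (four conditions, n = 30, assumed effect 0.8 SD, alpha 0.001):

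| b | Plain paired test | With linear position term |
|---|---|---|
| 0 | 0.76 | 0.73 |
| 0.25 | 0.62 | 0.73 |
| 0.5 | 0.37 | 0.73 |

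The mean estimate is 0.80 throughout, with or without the term.

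**4. Carry-over: bias.** Let a restricted block add cB to the next block, and a control block add cC. With four conditions, control directly follows a restricted block in 3/4 of orders. A given restricted condition follows another restricted block in 2/4 and control in 1/4. The bias in PBFR minus control is

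(2/4)cB + (1/4)cC − (3/4)cB = −(cB − cC)/4.

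With two conditions it is (1/2)cC − (1/2)cB = −(cB − cC)/2. The half also applies with four conditions if residual effects accumulate over blocks. The bias is zero if cB = cC and reverses sign if cB < cC.

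For illustration, take an excess cB − cC of 20% to 40% of the 0.7 SD effect, that is 0.14 to 0.28 SD. The contrast becomes 0.665 to 0.63 with four conditions and 0.63 to 0.56 with two. With no drift, power is 51% to 44% and 44% to 31%.

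**5. The position term does not touch this bias.** With a true effect of 0.80, cB = 0.4 and cC = 0, the simulated four-condition estimate is 0.70 both with and without it.

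**The case against.** The strongest reply is that order is randomised and rest is unrestricted, so the paired tests are valid as they stand. For drift, that is right on bias and on type I error; only precision is at issue. A reader might infer that fatigue over the visit pulls the contrast towards zero. The documents do not support that. Attenuation needs restriction to leave more residual effect than control. The metabolic-stress rationale in Protocol section 1.8 makes this plausible, but nothing in the documents measures it.

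A reader might also infer that conditions follow each other without recovery, that all four were always run, or that order was drawn without any balancing. The protocol allows as much rest as needed, four is a ceiling, and a balanced list is neither described nor excluded. The cuff-time limit in section 10.1 ("no longer than 20 minutes over the test period, divided into 6-7 minute intervals") roughly fits three restricted blocks of 6 to 7 minutes (18 to 21 minutes), but it does not show that three were run. The SAP's single PBFR condition leaves two conditions possible, and the two-condition losses are much smaller.

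Nor can the point be extended to the dose-response hypothesis H3. The SAP contains no dose-response test that could lose power; that omission is a separate matter.

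It is fair, too, that the size of the loss rests on assumed drift, and that the protocol classes the study as preliminary or exploratory (section 1.7). That lowers the stakes, but does not make it sensible to leave known order information unused.

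**Conclusion.** The point holds as one of precision. The paired analyses omit position in the order. Any drift across blocks then adds 3.33b² (four conditions) or 1.0b² (two) to the variance of the paired difference. For an assumed 0.7 SD effect at n = 30 and two-sided alpha 0.001, power of 57% becomes 55%, 41% and 24% with four conditions, or 57%, 52% and 43% with two, at b = 0.1, 0.3 and 0.5. The loss ranges from negligible to serious depending on a drift that the documents do not report. The t-test is only a stand-in for SPM, so these figures indicate relative loss rather than the study's actual power.

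Carry-over is a conditional caveat. If restriction leaves an excess residual effect, first-order carry-over shrinks the contrast by a quarter of that excess (four conditions) or a half (two). Neither its presence nor its direction is established.

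**What to change.** **Record the order.** Keep each participant's order of conditions in the analysis dataset, and state in the SAP how many conditions were run and which restriction level PBFR denotes.

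**Adjust for position.** With more than two conditions, replace the plain paired comparison with an SPM general linear model containing participant, condition and position, and analyse the ratings with adjustment for position too. With two conditions, compare period differences between the two orders, using SPM for the waveforms and the rank-sum test for the ratings.

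**Cost.** The order is already assigned, so this needs no new data provided it was recorded. It uses 1 to 3 degrees of freedom per model and gives slightly lower power if there is no drift (0.73 against 0.76 in the simulation above). The SAP is written in the past tense, so this may mean a re-analysis.

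**Carry-over.** The position term does not remove it. Report it as a limitation, or as an exploratory check where more than two conditions were run. With two conditions it is confounded with sequence. An analysis of first blocks only would compare 30/4, or about 7 to 8, people per condition between persons, with power of about 1% or less for the 0.7 SD effect at alpha 0.001 (assumed within-person correlation 0.5 to 0.8), so it could not settle the question.

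**Optional.** A balanced Williams set of orders could be used for participants not yet recruited. It balances position, but 30 per group is not divisible by four. Control still follows a restricted block in 3/4 of orders and a given restricted condition follows another in 2/4, so the carry-over asymmetry stays.
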